- d: Unscheduled visits may be conducted at any time that safety or safety MRI data indicate per protocol or as clinically indicated in the judgment of the investigator. Note that not all assessments indicated under UNS Visits need be conducted – actual assessments needed will be determined by the investigator and will be based on the specific visit needs.
- e: Only if clinically significant abnormalities are found at Visit 19 and the investigator considers it necessary to repeat at Visit 20. Clinical biochemistry, urinalysis, CBC, lymphocyte subsets and Igs should always be performed at Visit 20, regardless of clinical significance at the previous Follow-Up visit. (revised per Amendments 02 and 04)
- f: Measurements of body temperature and sitting blood pressure and heart rate will be obtained.
- g: Centralized skin assessments using standardized photography will be conducted by a reviewing dermatologist. These assessments will specifically include evaluation of any areas of depigmentation or any rash. Additional UNS dermatological assessments should be conducted in response to any dermatological AEs of concern (eg, depigmentation, rash, herpetic lesion).
- h: Examples of neurological signs that may indicate new central nervous system pathology that may need further investigation include (but not limited to) visual disturbance, dysarthria, dysphasia, muscle strength, limb weakness, hyperflexia, paraparesis, micturition difficulty or urgency or incontinence, ataxia, neuropsychiatric or cognitive decline in excess of expectations based on the subject's recent history. The Brief Smell Identification Test (Sensonics Inc.) will be administered at the same visits and serves as part of the neurologic examination. (revised per Amendment 04)
- i: If the subject experiences visual disturbances during the course of the study, the subject will be referred to a specialist for a further ophthalmic examination, which should include funduscopy to look at the optic disc, macula and the rest of the retina as well as an assessment of visual acuity and visual fields
- j: Please refer to [Section 9.4.7](#), which details prohibited and permitted medications in the study and associated timeframes.
- k: 12-lead standard ECGs will be recorded in triplicate (1 minute apart).

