7. Subjects who have a “yes” answer to the Columbia Suicide Severity Rating Scale (C-SSRS) suicidal ideation questions 4 or 5 at Visit 20 or Visit 21 or any suicidal behavior during the study prior to the start of the OLE Phase.
8. Female subjects of child bearing potential who meet any of the follow criteria:
 - a. Do not agree to use a highly effective method of contraception (eg, total abstinence, an intrauterine device, a double-barrier method [such as condom plus diaphragm with spermicide], a contraceptive implant, an oral contraceptive, or have a vasectomized partner with confirmed azoospermia) throughout the entire study treatment period and for 28 days after study drug discontinuation.
 - b. Are currently abstinent, and do not agree to use a double-barrier method (as described above) or refrain from sexually active during the study treatment period or for 28 days after study drug discontinuation.
 - c. Who do not agree to use the same contraceptive during the study treatment period or for 28 days after study drug discontinuation.
9. Females who are lactating or pregnant (as documented by a positive beta-human chorionic gonadotropin [β -hCG] or human chorionic gonadotropin [hCG] test with a minimum sensitivity of 25 IU/L or equivalent units of β -hCG or hCG) at Visit 20 or Visit 21.
10. Subjects with medical conditions (eg, cardiac, respiratory, gastrointestinal, renal disease) that are not stably controlled, or which, in the opinion of the investigator(s), could affect the subject’s safety or interfere with the study assessments.
11. Any other clinically significant abnormal findings in vital signs, ECGs and laboratory tests that would, in the investigator’s opinion, would affect the subject’s safety or interfere with study assessments during the OLE Phase.

STUDY DESIGN AND PLAN

The OLE Phase allows eligible subjects to receive elenbecestat (E2609) 50 mg for up to 24 months (2 years).

Subjects who are enrolled in the Core Study will have the option to participate in the OLE Phase provided that they complete the Core Study (which include 18 months of double-blind treatment and 12 weeks of Follow-up Period) and satisfy the entry criteria for the OLE Phase. Subjects who discontinue from study drug during the Core Study are not eligible to participate in the OLE Phase.

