Eligible subjects who choose to participate in the OLE Phase may enter the OLE Phase immediately following the completion of Visit 20 (ie, Visit 21 procedures may be completed on the same day as Visit 20). Subjects who are eligible to participate in the OLE Phase but who do not transition to the OLE Phase on the day of Visit 20 may enter the OLE Phase any time within 4 weeks of Visit 20. The Medical Monitor must be contacted if Visit 21 is to occur more than 4 weeks after Visit 20. For all subjects, assessments performed at V20 may serve as baseline values for the OLE Phase (ie, results of assessments conducted at Visit 21) with exceptions of laboratory assessments and vital signs, which must be repeated if Visit 21 occurs more than 10 days from Visit 20.

During the OLE Phase, subjects will receive open-label elenbecestat (E2609) 50 mg per day for up to 24 months. Subjects with pending INR and serum pregnancy test results (females subjects of child bearing potential only) but who are otherwise qualified may begin OLE dosing at Visit 21; however, these subjects must discontinue study drug treatment immediately if either test result meet the exclusion criteria.

Safety assessments will be performed as described in [Table 14](#). Subjects may discontinue from study drug for any reason. Subjects who complete 24 months of OLE treatment or who discontinue the study drug must comply with the Early Discontinuation Visit (within 7 days after the last dose of study drug) and the Follow-Up Visits (weeks 4 and 12 after the last dose of study drug).

The study will end when the last visit for the last subject has completed the OLE Phase.

Removal of Subjects from Therapy or Assessment

The investigator may discontinue study drug or withdraw the subject from the study at any time for safety or administrative reasons. The subject may decide to stop study drug or withdraw from the study at any time for any reason. Subjects who discontinue study drug prematurely for any reason will undergo an ED Visit within 7 days of their last dose of study drug. Subjects who discontinue from treatment during the OLE will have 2 posttreatment Follow-Up visits at 4 and 12 weeks after the last dose of study drug.

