- c: Blood samples for will be collected and stored. These samples may be used for exploratory biomarker analyses, or in the event that the subject develops treatment-emergent adverse events that warrant further investigation (eg, treatment-emergent infection), these samples may be tested to determine whether the subject already had prior exposure to any suspected infective agents.

STUDY DRUG SUPPLIES

Elenbecestat (E2609) tablets of 50-mg dose strengths will be supplied. Each subject will take 1 tablet per day.

SCHEDULE OF PROCEDURES/ASSESSMENTS

Table 14 presents the Schedule of Procedures/Assessments for the OLE Phase.

Table 14 Schedule of Procedures/Assessments in Study 202: Open-label Extension Phase

| Phase | Open-label Extension Phase | | | | | | | | | | | | | | | |
|---|----------------------------|----|----|----|----|-----|-----|-----|-----|-----|-----|-----|-----------------|------------------------|----------------|------------------------|
| | Treatment | | | | | | | | | | | | | Follow-Up ^d | | UNS Visit ^e |
| Period | 21 ^b | 22 | 23 | 24 | 25 | 26 | 27 | 28 | 29 | 30 | 31 | 32 | ED ^c | 33 | 34 | |
| Visit ^a | 1 | 2 | 3 | 4 | 5 | 6 | 7 | 8 | 9 | 10 | 11 | 12 | | 13 | 14 | |
| Day in OLE | 1 | 15 | 29 | 57 | 85 | 183 | 274 | 365 | 456 | 547 | 638 | 729 | | 757 | 813 | |
| Week in OLE | 1 | 3 | 5 | 9 | 13 | 27 | 40 | 53 | 66 | 79 | 92 | 105 | | 109 | 117 | |
| Weeks elapsed since 1st dose in OLE | 0 | 2 | 4 | 8 | 12 | 26 | 39 | 52 | 65 | 78 | 91 | 104 | | 108 | 116 | |
| Nominal months elapsed since first dose in OLE | 0 | | 1 | 2 | 3 | 6 | 9 | 12 | 15 | 18 | 21 | 24 | | 25 | 27 | |
| Procedures/ Assessments | | | | | | | | | | | | | | | | |
| Routine physical examination with dermatologic review | X ^{f,g} | X | X | X | X | X | X | X | X | X | X | X | X | X | X ^h | X |
| Inclusion and Exclusion criteria | X | | | | | | | | | | | | | | | |
| Vital signs, including respiratory rate ⁱ | X ^j | X | X | X | X | X | X | X | X | X | X | X | X | X | X ^h | X |
| Weight | X ^f | | | | | | | X | | | | X | X | | | X |
| Neurological examination ^k | X ^f | | | | | X | | X | | X | | X | X | | X | X |
| Concomitant medications ^l | X ^m | X | X | X | X | X | X | X | X | X | X | X | X | X | X | X |
| 12-lead ECG ⁿ | X ^f | | | | X | X | | X | | X | | X | X | X | X ^h | X |
| Clinical biochemistry and urinalysis | X ^j | X | X | X | X | X | X | X | X | X | X | X | X | X | X | X |

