C-SSRS = Columbia Suicide Severity Rating Scale, ECG = electrocardiogram, ED = Early Discontinuation, FAQ = Functional Assessment Questionnaire (also known as the Functional Activities Questionnaire), MMSE = Mini Mental State Examination, MRI = magnetic resonance imaging, OLE = Open-label Extension, PBMC = peripheral blood mononuclear cell, PD = pharmacodynamics, UNS = unscheduled, vMRI = volumetric magnetic resonance imaging.

- a: A window of ± 3 days will be permitted for Visits 22 and 23. A window of ± 7 days will be permitted for Visits 24 and 25. A window of ± 10 days will be permitted for Visit 26 to 32 inclusive. A window of ± 3 days will be permitted for the Follow-Up Visits. If a permitted visit windows is used, every effort should be made to bring the subject back in line with the “weeks elapsed since 1st dose in OLE” at subsequent visits.
- b: Visit 21 may occur on the same day or within 4 weeks of Visit 20 date. The Medical Monitor must be contacted if Visit 21 is to occur more than 4 weeks after Visit 20. Informed consent must be obtained prior to performing Visit 21 assessments.
- c: Subjects who discontinue taking study drug prematurely for any reason will undergo an ED Visit within 7 days of their last dose of study drug. In addition, Follow-Up Visits will be scheduled 4 and 12 weeks after the last dose of study drug (Visits 33 and 34 respectively).
- d: All subjects, regardless of whether they complete all 24 months of treatment or discontinue study drug prematurely, will complete the 2 posttreatment Follow-Up Visits; (ie, Visits 33 and 34). If clinically indicated, more frequent safety assessments can be made as UNS assessments or visits during the posttreatment Follow-up Period.
- e: Unscheduled visits may be conducted at any time that additional assessments, including MRI scans, are clinically indicated in the judgment of the investigator. Note that not all assessments indicated under UNS Visits need be conducted – actual assessments needed will be determined by the investigator and will be based on the specific visit needs.
- f: Result from Visit 20 will also serve as Visit 21 result. If the specified assessment was not performed at V20, it must be performed at Visit 21.
- g: Dermatologic assessment by the investigator must be performed at Visit 21 in addition to the centralized skin assessment (using standardized photography) performed at Visit 20.

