- h: Only if clinically significant abnormalities are found at Visit 33 and the investigator considers it necessary to repeat at Visit 34.
- i: Measurements of body temperature and sitting blood pressure and sitting heart rate will be obtained.
- j: Result from Visit 20 will also serve as Visit 21 result if Visit 21 occurs within 10 days from Visit 20. If Visit 21 occurs more than 10 days after Visit 20, the assessment must be repeated at Visit 21.
- k: Examples of neurological signs that may indicate new central nervous system pathology that may need further investigation include (but not limited to) visual disturbance, dysarthria, dysphasia, muscle strength, limb weakness, hyperflexia, paraparesis, micturition difficulty or urgency or incontinence, ataxia, neuropsychiatric or cognitive decline in excess of expectations based on the subject’s recent history. The Brief Smell Identification Test (Sensonics Inc.) will be administered at the same visits and serves as part of the neurologic examination.
- l: Please refer to Section 9.4.7 which describes prohibited and permitted medications in the study.
- m: Result from Visit 20 will also serve as Visit 21 result if Visit 21 occurs on the same day as Visit 20. If Visit 21 occurs more than 1 days after Visit 20, the assessment must be repeated at Visit 21.
- n: Single 12-lead standard ECGs will be recorded. If the QTcF is greater than 450 ms, perform 2 more 12-lead standard ECGs 1 minute apart and take the mean of the 3 QTcF values.
- o: Reports of the lymphocyte subset analyses will be sent to the Sponsor only. Lymphocyte subsets will include but are not limited to the following cell surface marker assessments: CD4 [T helper cells], CD8 [cytotoxic T cells], CD19 [B cells], CD16/CD56 [NK cells] and CD14 [macrophages] and absolute lymphocytes. Regulatory T cells will also be measured. Viability staining may also be employed.
- p: PD blood samples should be collected at fasting or at least 2 hours after the most recent meal and, as far as is feasible, samples should be taken at the same time of day. All PD blood samples should be collected predose.
- q: If dipstick urinalysis performed at site is abnormal, a urine sample will be sent to the central laboratory for full urinalysis.

-

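### For OLE entry within 10 days of Visit 20, neither schedule table explicitly requires blood pressure, heart rate, temperature or respiratory rate at Visit 20 or Visit 21 unless Visit 19 was abnormal

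*Protocol*

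**What the plan says.** **Core schedule (Section 9.5.2.1, Table 7).** Vital signs (temperature, sitting blood pressure and heart rate) and respiratory rate are unconditional at Visit 19, blank at the Week 8 follow-up visit, and marked with footnote e at Visit 20. Footnote e reads: "Only if clinically significant abnormalities are found at Visit 19 and the investigator considers it necessary to repeat at Visit 20". It then lists what is exempt from that condition: "Clinical biochemistry, urinalysis, CBC, lymphocyte subsets and Igs should always be performed at Visit 20, regardless of clinical significance". That list holds laboratory tests only.

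**OLE schedule (Appendix 6, Table 14).** The row "Vital signs, including respiratory rate" is marked at Visit 21 with footnote j. Within 10 days, "Result from Visit 20 will also serve as Visit 21 result if Visit 21 occurs within 10 days from Visit 20". Otherwise, "If Visit 21 occurs more than 10 days after Visit 20, the assessment must be repeated at Visit 21". Other Visit 21 rows, including ECG, weight and physical examination, carry footnote f, which adds: "If the specified assessment was not performed at V20, it must be performed at Visit 21".

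**Text.** Appendix 6 (Study Design and Plan) states that "assessments performed at V20 may serve as baseline values for the OLE Phase", with laboratory tests and vital signs to be redone if the gap exceeds 10 days. Section 9.1.3 gives the same rule and allows Visit 21 on the day of Visit 20. It also says vital signs are followed at each scheduled OLE visit.

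**Use of the data.** OLE exclusion 11 covers "Any other clinically significant abnormal findings in vital signs, ECGs and laboratory tests" that would affect safety or interfere with assessments. Vital signs are named in the OLE primary (safety) endpoint and are summarised as change from baseline.

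**The concern.** Footnote j hands Visit 21 over to a Visit 20 result that Table 7 often does not ask for. The 10-day rule speaks of repeating an assessment, which presupposes that it was done once. For a subject unremarkable at Visit 19 who moves straight into the OLE, a site reading the two tables literally would take no vital signs at either visit and then give the first OLE dose at Visit 21.

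Two things are at stake. First, exclusion 11 would be judged on vital signs about two months old. Second, any OLE baseline defined as the Visit 20/21 value would be absent mainly in subjects who were normal at Visit 19, so missingness would depend on an earlier result. An analysis plan can choose among existing values but cannot recover measurements that were never taken.

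**Working it through.** No sample size, power or error rate is involved. The check is to follow the affected subject through both tables.

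**Step 1. Which rows combine a conditional Visit 20 with a footnote that has no fallback?**

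| Assessment | Visit 20 (Table 7) | Visit 21 (Table 14) | Measured at 20 or 21 by explicit rule? |
|---|---|---|---|
| BP, heart rate, temperature | conditional (e) | j, no fallback | not if Visit 19 was normal and gap is 10 days or less |
| Respiratory rate | conditional (e) | j, no fallback | same |
| ECG | conditional (e) | f, with fallback | yes |
| Weight | unconditional | f, with fallback | yes |
| Biochemistry, urinalysis, CBC, lymphocyte subsets | always done (e, second sentence) | j, no fallback | yes |

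Of these rows, only vital signs and respiratory rate fall through. The ECG row shows that the protocol foresaw the case of a Visit 20 assessment not being done and covered it. The laboratory rows carry footnote j safely because footnote e makes them mandatory at Visit 20.

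**Step 2. Who is affected?** Two conditions apply together:
- footnote e was not triggered: either no clinically significant abnormality at Visit 19, or one that the investigator did not think needed repeating;
- Visit 21 falls 0 to 10 days after Visit 20, same-day entry included.

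Beyond 10 days, footnote j requires measurement and the gap closes.

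**Step 3. How old is the last required set?** From the Table 7 headers, Visit 19 is 82 weeks and Visit 20 is 90 weeks after first dose.
- Gap to Visit 20: 90 − 82 = 8 weeks. The day numbers agree: 631 − 575 = 56 days.
- Gap to the first OLE dose at Visit 21: 56 + 0 = 56 days to 56 + 10 = 66 days.

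These are nominal times; visit windows of ±3 days apply to the follow-up visits.

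**Step 4. Does other text settle it?** Section 9.1.3 has vital signs at each scheduled OLE visit, which points to measuring at Visit 21. The same section also contains the 10-day reuse rule. The protocol therefore gives two instructions for the same subject, and two sites could each follow it and return different data.

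**The case against.** The strongest reply is that the protocol does not leave Visit 21 empty. The cell is marked; footnote j only substitutes a Visit 20 result, and where there is none the mark arguably stands. The text refers to assessments actually performed at Visit 20 and says that they may serve, which is permissive. Section 9.1.3 calls for vital signs at each scheduled OLE visit. Eligibility review is an unfootnoted item at Visit 21, and exclusion 11 gives a further reason to measure. A careful site would probably do so. This reply stands so far as it shows that measurement is allowed and arguably intended. It does not remove the conflict, because footnote j never says what to do when Visit 20 has no result, and footnote f does.

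A reader might go further and infer that most OLE entrants have no baseline vital signs, and that the OLE change-from-baseline summary therefore rests on a selected subset open to regression to the mean. The documents do not support that:
- Nothing gives the share entering within 10 days. Entry is allowed over 4 weeks, or later after contact with the Medical Monitor.
- Weight, which Section 9.5.1.5.4 counts among vital sign measurements, is unconditional at Visit 20.
- The OLE safety analysis refers only to change from baseline, without saying whether the Core or the OLE baseline is meant; the OLE secondary endpoints name both. Core baseline vital signs are scheduled for every subject, and a rule taking the last value before the first OLE dose could use Visit 19.

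**Conclusion.** The point holds as an inconsistency between the two schedule tables, and between footnote j and both Section 9.1.3 and exclusion 11. For subjects who did not trigger footnote e and who enter within 10 days, neither table explicitly requires blood pressure, heart rate, temperature or respiratory rate at Visit 20 or Visit 21. The last required set is nominally 56 to 66 days before the first OLE dose.

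The consequences are conditional. If sites follow footnote j literally, entry vital signs will be missing mainly in subjects who were normal at Visit 19, and exclusion 11 will be applied without current values. Distortion of the change-from-baseline summary needs one further assumption, that the analysis accepts only a Visit 20/21 baseline. The protocol does not say so. How many subjects are affected cannot be worked out from it.

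This is minor: OLE safety is summarised descriptively, no sample size is calculated for the OLE, and the remedy is small. It is still worth correcting in the protocol, because the values cannot be obtained afterwards.

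**What to change.** Reconcile Table 7 footnote e, Table 14 footnote j, Section 9.1.3 and the matching paragraph of Appendix 6. The simplest change is to attach footnote f's existing sentence to the Visit 21 vital signs row: "If the specified assessment was not performed at V20, it must be performed at Visit 21". The 10-day rule can stay as it is for subjects who do have a Visit 20 result.

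The cost is one sentence in a footnote and a few minutes at a visit the subject already attends. The laboratory rows that share footnote j need no change.

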| Subjects currently receiving 5 or 15 mg E2609 will be re-assigned to 50 mg E2609 for the remainder of the double-blind treatment period provided they will receive at least 12 weeks of double-blind treatment after the re-assignment, (ie, no dose reassignments past Visit 17). | As E2609 50 mg has been selected as the appropriate dose for Phase 3 development, subjects should not continue with doses that are not being advanced clinically. Additionally, the re-assignment of subjects in E2609 5 and 15 mg to E2609 50 mg will further the safety and tolerability data in subjects exposed to E2609 50 mg. | 
Synopsis
 
 • Study Design • Number of Subjects • Sample Size Rationale 
Section 7.1 Section 9.1 Section 9.1.2.1 Section 9.4.1 Section 9.4.4 Section 9.5.2
 |
| Clarified that one of the exploratory endpoints will analyze change from baseline in CSF amyloid and CSF BACE1 measurements from 4 weeks and up to 18 months of treatment only. There will no analysis for treatment follow-up. | Correction | 
Synopsis
 
 • Analysis for Exploratory Endpoints • Exploratory Objective 
Section 8.3 Section 9.7.1.1.3 Section 9.7.1.6.3
 |
| The frequency of DSMB safety reviews after the 12 week interim safety analysis will be reassessed and details will provided in the DSMB charter. | The DSMB charter will provide full details of interim safety reviews. | 
Synopsis
 
 • Study Design 
Section 9.1
 |
| Removed the statement that subjects must be stable on AChEI or memantine to be included in the primary analyses. | This statement is no longer relevant as of Amendment 05. | 
Synopsis
 
 • Concomitant Drug/Therapy 
Section 9.4.7
 |
| Added a statement to specify that additional analyses will be performed for subjects with dose re-assignment and details of these analyses and | To clarify that the SAP will be finalized prior to database lock and it will provide full details of the analyses to be performed for this study. | Section 9.7.1 |

Revisions to Version 7.0

New version/date: Version 8.0 / 02 Nov 2016 (per Amendment 06)

| Change | Rationale | Affected Protocol Sections |
|---|------------------|-----------------------------------|
| treatment group definitions will be provided in the statistical analysis plan (SAP); clarified that the SAP will be finalized before database lock. | | |
| Grammatical, typographical, and formatting changes | | Throughout |

Revisions to Version 6.0

New version/date: Version 7.0 / 26 Sep 2016 (per Amendment 05)

| Change | Rationale | Affected Protocol Sections |
|---|--|---|
| Grammatical, typographical, and formatting changes | | Throughout |
| Removed Stage B from protocol. In line with this decision, the study objectives and endpoints have been modified and subjects who discontinue study drug early for any reason will no longer be required to complete efficacy visits after last dose of study drug. | This study will no longer be a Proof-of-Concept study. | Synopsis 
 • Study Protocol Title • Investigators • Sites • Study Period and Phase of Development • Objectives • Study Design • Early Discontinuation • Number of Subjects • Study Treatments • Efficacy Assessments • Safety Assessments • Statistical Methods • Study Endpoints • Analysis Sets • Efficacy and Biomarker Analyses • Analysis for the Primary/Secondary/Exploratory Endpoints • Pharmacokinetic Analyses • Pharmacokinetic /Pharmacodynamic Analyses • Interim Analyses • Sample Size Rationale Section 6 Section 7 Section 8 Section 8.3 Section 9.1 Section 9.2.1 Section 9.2.3 Section 9.2.4.4 Section 9.2.5 Section 9.3 Section 9.4.3 |

Revisions to Version 6.0

New version/date: Version 7.0 / 26 Sep 2016 (per Amendment 05)

| Change | Rationale | Affected Protocol Sections |
|-----------------------------------|--|--|
| | | Section 9.4.4 Section 9.4.7 Section 9.2.5 Section 9.5.1.3.1 Section 9.5.1.4.2 Section 9.5.1.5.1 Section 9.5.2 Section 9.5.4.1 Section 9.5.5 Section 9.7 Section 10 |
| Updated Eisai contact information | Change in personnel and move to Building 100 | 
 • Title Page • Protocol Signature Page |

Revisions to Version 5.0

New version/date: Version 6.0 / 29 Jun 2016 (per Amendment 04)

| Change | Rationale | Affected Protocol Sections |
|--|---|---|
| Revised number of investigational sites (from 40 to 35) | Feasibility | 
 • Synopsis - 
 ○ Study Design ○ Sites • Section 6 • Section 9.1 • Section 9.3 |
| Removed Exclusion Criterion No. 44 for male subjects regarding restrictions on child bearing | No longer a safety concern; E2609 has not shown a deleterious effect on sperm in preclinical reproductive toxicity studies. | 
 • Synopsis: 
 ○ Exclusion Criteria • Section 9.3.2 |
| Added option for subjects who provided a CSF sample prior to randomization but who declined the CSF sample collection after 4 weeks of dosing to provide a postdose CSF sample at any point in the study (ie, even after 4 weeks of dosing). | Reflects the added value of CSF data for the PK/PD secondary objective of this study. In addition, given that PK steady state is achieved within the 1st 2 weeks of initiation of dosing, data collected post Week 4 visit is still considered to be applicable in assessment of the steady state effect. | 
 • Synopsis - 
 ○ Pharmacodynamic Assessments • Section 5.3 • Section 9.1 • Section 9.1.1.2 • Section 9.5.1.3.3 • Section 9.5.1.4 • Table 6 • Table 7 • Table 8 |
| Revised details of restrictions to anticoagulant therapy and short-term steroid use revised/moved details regarding antiplatelet drugs to the main body of the protocol | To assist in subject recruitment and retention and considering that the strict restrictions were not necessary for subject safety | 
 • Synopsis - 
 ○ Concomitant Drug/Therapy • Section 9.4.7 • Appendix 2 |
| Removed the >33% decrease from baseline for CD4, CD8, and CD19 as a trigger for more frequent testing of flow cytometry and CBCs. Additional safety monitoring for CD4, CD8, CD19, and CBCs will only be based on the population adjusted LLNs for clinically asymptomatic subjects. | Experience to date has indicated significant variability within the normal range, both for increases and decreases. Absolute counts of lymphocyte subsets are more meaningful than percentage decreases for triggering more frequent monitoring. | 
 • Section 9.3.3 • Table 1 • Table 2 |

Revisions to Version 5.0

New version/date: Version 6.0 / 29 Jun 2016 (per Amendment 04)

| Change | Rationale | Affected Protocol Sections |
|---|--|--|
| 
Added option to temporarily suspend study drug for subjects who are clinically asymptomatic but who meet CD4, CD8, or CD19 discontinuation thresholds on 2 consecutive tests. Introduce rules for ability to re-start study drug (ie, rechallenge) in these subjects. Only 1 cycle of temporary suspension and rechallenge with study drug permitted for any individual subject.
 | 
To assist in subject retention and to gain knowledge on the behavior of lymphocyte subsets on rechallenge.
 | 
 • Section 9.3.3 • Table 1 • Table 2 |
| 
Added extra blood draw times with focus on lymphocyte subsets, CBCs, and immunoglobulins during the 12-week safety follow-up for all subjects.
 | 
To increase frequency of key safety monitoring parameters in post-treatment follow-up period so as to assess immunological changes after completion of study drug
 | 
 • Synopsis 
 ○ Study Design ○ Safety Assessments • Section 9.1.2.2 • Section 9.1.2.3 • Section 9.2.5 • Section 9.3.3 • Table 7 • Table 8 • Section 9.5.1.5.7 • Section 9.5.5 |
| 
Clarified that the Functional Assessment Questionnaire is to be administered to the informant/caregiver, and not the subject.
 | 
Clarification
 | 
 • Synopsis 
 ○ Efficacy Assessments • Section 9.5.1.3.1 |
| 
Added clarification that the Brief Smell Identification Test will be administered as part of the neurological examination
 | 
Clarification
 | 
 • Synopsis 
 ○ Safety Assessments ○ Interim Analyses • Section 9.1.1.2 • Section 9.5.1.2.1 • Section 9.5.1.5.9 • Table 6 • Table 7 |

Revisions to Version 5.0

New version/date: Version 6.0 / 29 Jun 2016 (per Amendment 04)

| Change | Rationale | Affected Protocol Sections |
|--|--|---|
| Revised number of randomized subjects in Stage A to n=60±20% | To allow for additional randomization based upon current number of subjects in screening at the time of amendment implementation | 
 • Synopsis 
 ○ Study Design ○ No. of Subjects • Section 7 • Section 9.1 • Section 9.2.1 • Section 9.2.5 • Section 9.3 • Section 9.7.3 |
| Grammatical, typographical, and formatting corrections | Consistency | various |

Revisions to Version 4.0

New version/date: Version 5.0, 06 Feb 2016 (per Amendment 03)

| Change | Rationale | Affected Protocol Sections |
|---|--|--|
| Add interim analyses of safety, and PK/PD data throughout Stage A | Decision making regarding the remainder of the study and the full E2609 clinical development program | 
• Synopsis –
○ Exploratory Endpoint Analysis○ Interim Analysis• Section 9.1• Section 9.1.1.2• Section 9.4.6• Section 9.7.1.7.1 |

Revisions to Version 3.0

New version/date: Version 4.0, 05 Nov 2015 (per Amendment 02)

| Change | Rationale | Affected Protocol Sections |
|--|--|---|
| Grammatical, typographical, and formatting changes | | Throughout |
| Mandatory nature of CSF collection in study changed to voluntary. This change impacts the timing and details of the PK/PD interim analyses. It also impacts the nature of the CSF-related objectives, which will now be identified as exploratory. | To increase rate of subject consent into the study | 
 • Synopsis – 
 ○ Secondary Objectives ○ Exploratory Objectives ○ Study Design ○ Exclusion Criterion No. 12 ○ Pharmacokinetic Assessments ○ Pharmacodynamic, Pharmacogenomic, and Other Biomarker Assessments ○ Safety Assessments ○ Secondary Endpoints ○ Exploratory Endpoints ○ Analysis for the Secondary Endpoints ○ Analysis for the Exploratory Endpoints • Section 5.3 • Section 8.2 • Section 8.3 • Section 9.1 • Section 9.1.1.2 • Section 9.2.5 • Section 9.3.2 • Section 9.4.6 • Section 9.5.1.3.3 • Section 9.5.1.4 • Section 9.5.1.5.12 • Section 9.7.1.1.2 • Section 9.7.1.1.3 • Section 9.7.1.6.2 • Section 9.7.1.6.3 • Appendix 2, Listing 2 |

Revisions to Version 3.0

New version/date: Version 4.0, 05 Nov 2015 (per Amendment 02)

| Change | Rationale | Affected Protocol Sections |
|--|---|--|
| Extended the range of cognitive impairment in delayed recall that would be considered inclusionary for the study and removed the eligibility nature of the cognitive tests repeated at the Baseline Visit. | Original delayed recall aspect of inclusion criterion #1 was considered to be too restrictive and was unnecessarily screening out subjects with MCI/prodromal AD. The eligibility nature of the cognitive tests repeated at the Baseline Visit has been removed in order to simplify the requirements of the pretreatment period for the study. | 
 • Synopsis – 
 ○ Inclusion/Exclusion Criteria • Section 9.3.1 • Section 9.3.2 |
| Addition of historical amyloid PET scans for determination of eligibility for the study. Subjects with historical PET scans will not be part of the longitudinal PET analyses and therefore will not require a second PET scan at either Visit 18 or ED. | To provide the sites with greater operational flexibility and reduce subject burden. | 
 • Synopsis – 
 ○ Inclusion/Exclusion ○ Pharmacodynamic, Pharmacogenomic, and Other Biomarker Assessments • Section 9.1.1 • Section 9.2.4.3 • Section 9.3.1 • Section 9.5.2 • Table 6 • Table 7 |
| Added the need for safety laboratory tests to be repeated for subjects whose pre-treatment period is extended due to active infection. | To ensure that all baseline safety laboratory tests are repeated for subjects whose pretreatment period is extended. | 
 • Synopsis – 
 ○ Inclusion/Exclusion • Section 9.3.2 • Section 9.5.2 • Table 6 |
| Clarified that exclusion criterion No. 22 (exclusion of subjects with CD4, CD8, or CD19 absolute counts below the LLN) applies to flow cytometry tests conducted at both the Screening and the Baseline Visits. Furthermore, LLNs that are adjusted for the subject population under study will be used. | It was not clear that Exclusion Criterion No. 22 applied to both the Screening and the Baseline Visits. The LLNs for CD4, CD8 and CD19 absolute counts require adjustment for the age of the patient population in this study. | 
 • Synopsis – 
 ○ Inclusion/Exclusion Criteria • Section 9.3.2 |
| Provided additional detail | Added to provide clarity | 
 • Synopsis – |

Revisions to Version 3.0

New version/date: Version 4.0, 05 Nov 2015 (per Amendment 02)

| Change | Rationale | Affected Protocol Sections |
|--|---|---|
| regarding scope of Exclusion Criterion No. 34 which excludes subjects with hypopigmentation conditions. | for the sites. | 
 ○ Exclusion Criteria ● Section 9.3.2 |
| Revised number of clinical sites from 30 to 40 | For feasibility purposes | 
 ● Synopsis – 
 ○ Sites ● Section 6 ● Section 9.1 ● Section 9.3 |
| Relaxed the requirement for the cognitive assessments at Screening Visit 1 to be conducted in a certain order and revised the recommended order in which the assessments could be conducted. | To provide the sites with greater operational flexibility. | 
 ● Section 9.1.1 ● Figure 2 ● Section 9.5.1.3.1 ● Section 9.5.2 ● Table 6 |
| Clarify the duration for which the Safety magnetic resonance imaging (MRI) scan, the amyloid PET scan and the lumbar puncture (LP) collected CSF conducted at Screening are considered valid. | To provide sites with greater operational flexibility, particularly for re-screening of screen fail subjects. | 
 ● Section 9.1.1 |
| Clarify that for subjects meeting criteria for weekly monitoring of lymphocyte subsets, these can be accommodated within the scheduled clinic visits during the early stages of the treatment period of the study. | To provide operational clarity to the sites. | 
 ● Synopsis – 
 ○ Exclusion Criteria ● Section 9.3.2 ● Section 9.3.3 ● Section 9.5.1.5.3 |
| Added the requirement for complete blood counts (CBC) with differentials to be performed whenever repeat or unscheduled flow cytometry tests are performed. | Such that CBC data are available at all times when flow cytometry data is available. | 
 ● Section 9.3.3 ● Table 1 ● Section 9.5.2 ● Table 6 ● Table 7 |

Revisions to Version 3.0

New version/date: Version 4.0, 05 Nov 2015 (per Amendment 02)

| Change | Rationale | Affected Protocol Sections |
|---|---|--|
| Added 30 day window to the duration of the pre-treatment period if required for medical or operational reasons. | To provide the sites with greater operational flexibility. | 
 • Synopsis – 
 ○ Study Design ○ Duration of Treatment • Section 9.1 • Figure 1 • Section 9.1.1 • Section 9.1.1.2 • Section 9.5.2 • Table 6 |
| Clarified the timing of the start of the Randomization Phase | Clarification | 
 • Section 9.1.1 • Section 9.1.2 • Section 9.5.2 • Table 6 • Table 7 |
| Increased number of MCI/Prodromal or mild to moderate AD subjects screened for entry into the study | To reflect the higher screen failure rate than originally anticipated | 
 • Synopsis – 
 ○ Number of Subjects |
| Removal of CD127 cell surface markers | FoxP3 is the most accepted marker to measure T regulatory cells and additional assessment of CD127 is not required. | 
 • Section 9.5.1.5.3 • Table 4 • Section 9.5.2.1 |
| Made the clinical biochemistry, urinalysis, CBC, lymphocyte subsets, and immunoglobulin tests mandatory at Visit 20, regardless of clinical significance at Visit 19. | For more comprehensive safety data at the second follow-up visit. | 
 • Section 9.5.2 • Table 7 |
| Corrected reference to Exclusion Criterion No. 20 (and not to Exclusion #19) in footnote to Table 6 and Table 7 regarding timing of Visit 3 in relation to Visit 2. | Correction | 
 • Section 9.5.2 • Table 6 • Table 7 |
| Revised details regarding prohibited antiplatelet drugs | To distinguish between those subjects who consent to CSF sample collection and those who do not | 
 • Appendix 2, Listing 2 |

Revisions to Version 2.0

New version/date: Version 3.0, 28 May 2015 (per Amendment 01)

| Change | Rationale | Affected Protocol Sections |
|--|--|---|
